5.3 Neurophysiological Indices of Cortical Inhibition in the DLPFC

TMS-EEG will be used to evaluate neurophysiological measures from the DLPFC prior to and after a course of either ECT or MST treatment. TMS will be administered to the left DLPFC using two Magstim-200 stimulators (Magstim Company Ltd., UK) connected via a Bistim module and electrophysiological data will be collected using dedicated hardware and software (Neuroscan, Compumedics, USA). Each TMS session will include the establishment of the individual threshold for stimulation, followed by cortical inhibition paradigms in the DLPFC according to our previously published methods [63]. Identification of the DLPFC will be conducted in a manner that is identical to those during rTMS treatment. Recordings will be acquired through a 64-channel electroencephalography (EEG). Neurophysiological indices from the DLPFC (e.g., N100 and LIC1) will be the dependant variables of interest and derived according to previous publications [63, 66]. Prior to study start, the teams at UT Southwestern and UCSD will set up a laboratory with the necessary equipment and materials, and will be trained on the methods of the proposed experiment. A neurophysiology expert from the Temerty Centre at CAMH will be visiting UT Southwestern and UCSD to ensure that the TMS-EEG recordings are compatible between sites.

Variability between sites is low as previous trials between CAMH and Melbourne, Australia have shown comparable measures between these three sites. Neurophysiological data will be collected and coded by experienced raters who will be blind to treatment status. Data analysis will take place at CAMH using semi-automated methods developed and validated by our group.

5.4. Resting EEG and Multi-Scale Entropy

Ten minutes of resting-state eyes closed EEG data are recorded prior to the start and after a course of ECT or MST treatment. EEG will be through a 64-channel NeuroScan EEG system. Acquired data will be imported into MATLAB (The MathWorks. Inc. Natick, MA, USA) for preprocessing. The open source signal processing functions in EEGLAB toolbox will be used for data import and preprocessing. Multi-scale entropy will be examined across all electrodes using two steps [101]: The *coarse-graining* process and the calculation of the sample entropy (*SampEn*) for each coarse-grained time series. First, for a given time series $\{x_1, x_2, \dots, x_N\}$, the multiple coarse-grained time series $\{y_1^{(\tau)}, y_2^{(\tau)}, \dots, y_N^{(\tau)}\}$ at scale factor τ are calculated by averaging the data points within non-overlapping windows of increasing length τ . Each element of the coarse-grained time series $y_j^{(\tau)}$, will be calculated as $y_j^{(\tau)} = \frac{1}{\tau} \sum_{i=(j-1)\tau+1}^{j\tau} x_i$, where τ represents the scale factor and $j \left(1 \leq j \leq \frac{N}{\tau}\right)$ represents the time index of the element. The length of each coarse-grained time series is M , where $M = \text{floor} \left(\frac{N}{\tau}\right)$. Second, the degree of predictability is measured for each of the multiple coarse-grained time series $\{y_1^{(\tau)}, y_2^{(\tau)}, \dots, y_N^{(\tau)}\}$ using SampleEn. SampleEn is calculated as $\text{SampleEn}(r, m, M) = -\ln(C(m+1)/C(m))$, where $C(m)$ is the total number of pairs of m consecutive similar data points, $C(m+1)$ is the total number of pairs of $m+1$ consecutive similar data points in the multiple coarse-grained time series. SampleEn quantifies the variability by estimating the predictability of amplitude patterns across a time series. Two consecutive data points will be used for data matching ($m = 2$) and data points will be considered to match if their absolute amplitude difference is less than 0.15% ($r = 0.15$) of standard deviation of time series. Multi-scale entropy will be calculated for two 20s continuous epochs according to Farzan et al. and then averaged [102].

5.5 Discontinuation of Treatment Criteria

Participants will be discontinued from the treatment if they cannot continue the study safely based on any of the following criteria:

- (1) experience worsening in depression, defined as an increase in HRSD-24 score from baseline of more than 30% on two consecutive assessments;
- (2) experience clinically significant increase in suicidal ideation with imminent intent (based on the SSI) or attempt suicide;
- (3) develop clinically significant hypomanic or manic symptoms
- (4) withdraw consent
- (5) missed seizures (i.e. no induced seizure) on 2 consecutive treatment sessions despite parameter and anaesthesia optimization
- (6) non-compliant with treatment schedule (i.e. miss more than two scheduled treatments)

Participants who are non-compliant with the treatment regimen or who experience two missed seizures on two consecutive occasions despite optimization of anesthesia and treatment parameters will not be discontinued from the trial, but will continue to be followed and will complete assessments to the extent possible contingent upon patient agreement consistent with an intention to treat approach.

Patients who are not able to complete the biomarker testing will be able to complete the clinical portion of the trial and will not be excluded.

5.6 Participant Discontinuation/Withdrawal from the Study

Participants will be discontinued from the study if they meet any of the following criteria:

- (1) withdraw consent
- (2) the Principal Investigator believes that for safety reasons it is in the best interest of the participant to stop participation
- (3) are non-compliant with study visits and assessments
- (4) participant engages in serious attempt to harm others
- (5) emergence of catatonia

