5.1.5 Clinical and Cognitive Measures

Screening and Baseline evaluation:

Prior to screening, potential participants will be seen for a consultation by an ECT/MST attending psychiatrist. Capacity to consent to treatment and research procedures will be assessed and documented. Participants will be screened with the MINI V 6.0 and HRSD-24 to determine eligibility. The MINI V 6.0 assesses current and lifetime depression and other psychiatric disorders. It will be used to clarify psychiatric inclusion and exclusion criteria. Furthermore, a score of greater than or equal to 21 on the HRSD-24 will be used to establish eligibility. The Transcranial Magnetic Stimulation Adult Safety Screen will be used to assess for potential MST risk factors[75]. The Antidepressant Treatment History Form (ATHF) will be used to quantify level of treatment resistance[77, 78]. Demographic information, medical history and concomitant medications information will also be collected at the screening visit. The Clinical Global Impression Scale-Severity (CGI-S)[46] and Young Mania Rating scale (YMRS) will also be completed at baseline. The schedule of assessments is depicted in Table 1 (Appendix A).

Clinical Assessments During and After Treatment:

Clinical outcome measures will be completed at baseline, after every three treatments (or every four treatments to facilitate treatment scheduling) immediately prior to the next treatment session, within four days of the last treatment session, and then six months post-treatment. This latter time point will be part of an exploratory analysis to study the long-term clinical and cognitive outcomes post- ECT or post-MST treatment. The HRSD-24 [74] will be the primary outcome measure. Secondary outcome measures will include the Scale for Suicidal Ideation (SSI)[69], Brief Symptom Inventory (BSI)[79], Clinical Global Impression Severity/Improvement Scale (CGI-S, CGI-I)[80], Quality of Life Enjoyment and Satisfaction Questionnaire (Q-LES-Q)[81], and the Columbia ECT Subjective Side Effects Schedule[82].

Cognitive Assessments

The cognitive battery was designed to comprehensively examine cognitive dimensions that are affected by seizure therapies while minimizing burden on participants[23]. Assessments included in the cognitive battery measure global cognitive function, intellectual abilities, attention, processing speed, verbal fluency, anterograde and retrograde memory, and executive functions. Specific cognitive measures include:

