The hypothesis to be tested is $H_0: \pi_{ECT} - \pi_{MST} \geq 0.15$ versus $H_1: \pi_{ECT} - \pi_{MST} < 0.15$ where π_{ECT} and π_{MST} are the probabilities of remission in the ECT and MST groups respectively. The primary comparison will be a one-sided Z-test in difference of proportions, compared against the non-inferiority margin of 15%. The 15% non-inferiority margin was chosen as a remission rate of 35% remains clinically meaningful in this difficult to treat sample and still higher than more conventional, less invasive treatments for treatment resistant depression (e.g., rTMS at about 20 percent remission [106] and 14 percent with antidepressants [107]). The absolute risk difference (difference in proportions) will be calculated along with 90% and 95% confidence intervals, using standard normal approximations. Since intention to treat (ITT) analysis introduces a conservatism that is undesirable for non-inferiority trials both ITT (i.e. all randomized participants) and completer analyses (i.e. 8 treatments or met remission criteria) will be performed. The primary analysis for Stage 1 will be a completer analysis and a sensitivity analysis will be done secondarily. Inverse probability weighted methods will be employed in an attempt to attenuate the bias resulting from the improper sub-group that a PP results in. We plan to collect the primary outcome data from all patients regardless of treatment compliance to minimize missing data in the outcomes. If outcomes are missing in more than 5% of the patients in the ITT analysis, inverse probability weighting and multiple imputation approaches will be employed to assess and mitigate the effect of missing data. Multiple Imputation by Chained Equations (MICE) will be used to perform the imputations and the following variables will be used in the missing data model: number of failed antidepressant trials, duration of most recent depressive episode, number of major depressive episodes, benzodiazepine use, age, and presence of the other psychiatric comorbidities, e.g. anxiety, duration of illness, not taking psychiatric medication at baseline, treatment duration, and minority racial status. The number of replications for multiple imputations will be based on the proportion of data that is missing, e.g. 10% missing implies 10 replications. For the inverse probability weighting, weights will be estimated from a logistic regression model (with binary dependent variable: dropout vs not dropout) predicting probability of dropout. In order to have a correctly specified model, most of the baseline variables collected will be included (e.g. demographic and clinical characteristics, HRSD score, SSI score, CGI score, ATHF, BSI score, presence of medical and/or psychiatric comorbidities, etc.). It is only necessary for non-inferiority to be established in the unadjusted analysis described to proceed to the stage 2 analysis although additional secondary analyses of this outcome will be performed.

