
An adjusted analysis will be performed using generalized linear models for binary data. Study site will be included as well as clinical variables known to be associated with remission (see again Senn et al.[105] and Pocock et. al.[104]). The following variables will be included in the analysis, which have been shown to be related to response/remission in this population: number of failed antidepressant trials, duration of most recent depressive episode, number of major depressive episodes, and benzodiazepine use (in lorazepam equivalents). The purpose of the adjusted analysis is to ensure the non-inferiority finding is consistent between an unadjusted analysis and one in which predictors of outcome are controlled for. This consistency will be examined in two ways. First, the unadjusted odds ratio and 95% confidence interval will be compared with the adjusted for consistency. Second, the fitted logistic regression model will be used to estimate the probability of response for each subject. An adjusted difference in proportions will be estimated by averaging the predicted probabilities within group and taking the difference. A bootstrap will then be used to generate a distribution of this measurement from which the bias corrected percentiles can be obtained to compare with the 15% non-inferiority margin.

Stage 2 Analysis

In terms of cognitive superiority, we will use the autobiographical memory test (AMT). The binary outcome is defined as a worsening of $\geq 25\%$ on the AMT total score. The hypothesis to be tested is $H_0: \pi_{ECT} - \pi_{MST} = 0$ versus $H_1: \pi_{ECT} - \pi_{MST} \neq 0$ where π_{ECT} and π_{MST} are the probabilities of deterioration in the ECT and MST groups respectively. This primary analysis will be ITT. The hypothesis will be tested with a chi-square test. The absolute risk difference and 95% confidence interval will be computed using standard methods. Secondary analyses will follow a similar approach as in stage 1.

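### Section 5.6 removes participants from the study for four reasons other than withdrawn consent and states no later outcome collection, so the ITT analyses can lose data that could have been sought

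*Combined protocol and SAP*

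**What the plan says.** The protocol separates stopping treatment (section 5.5) from leaving the study (section 5.6).

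Section 5.6 is mandatory: "Participants will be discontinued from the study if they meet any of the following criteria". Besides withdrawal of consent, the criteria are a safety judgement by the Principal Investigator, a serious attempt to harm others, catatonia, and participants who "are non-compliant with study visits and assessments". The section does not say what happens to outcome collection afterwards.

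Section 5.5 treats missed treatments differently. Its criterion (6) gives a limit, "non-compliant with treatment schedule (i.e. miss more than two scheduled treatments", and participants who meet it, or who have missed seizures at two consecutive sessions, "will not be discontinued from the trial, but will continue to be followed and will complete assessments to the extent possible", which the section ties to an intention-to-treat approach. It makes no such statement for criteria (1) to (3): worsening depression, increased suicidality and mania.

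Other text bears on the same question:

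- Section 5.8.1, Stage 1: "We plan to collect the primary outcome data from all patients regardless of treatment compliance to minimize missing data in the outcomes".
- Section 5.1.5 places clinical ratings "within four days of the last treatment session, and then six months post-treatment", and has the cognitive battery, including the AMT, done when treatment ends, early withdrawal from treatment included.
- Section 5.8.1 defines ITT as all randomized participants. For HRSD-24 remission, "The primary analysis for Stage 1 will be a completer analysis", with ITT also performed. For the AMT, "This primary analysis will be ITT".

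**The concern.** A participant who misses some assessments is someone from whom later assessments should still be requested. Section 5.6(3) does the reverse. With no number of missed visits stated, a participant who skips mid-course ratings could be removed before a post-acute visit that they might have attended. Intermittent missing data then become permanent.

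The AMT is the most exposed outcome. Section 5.1.5 and Table 1 schedule it at baseline, end of treatment and six months only. A participant removed mid-course may have no post-treatment AMT at all, yet still counts in the Stage 2 primary set. Stage 2 is one half of the combined primary endpoint. The Stage 1 ITT analysis and the exploratory six-month analysis are exposed in the same way.

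The reasons for removal (safety, non-attendance, catatonia) may be related to outcome and may differ between arms. The risk is therefore bias rather than lost precision, and analysis cannot fully repair data that were never sought.

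**Working it through.** **Text comparison.** The question is whether any other provision secures outcomes after a removal under section 5.6.

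| Provision | What triggers it | Stated to apply after study removal? | Secures the six-month visit for those removed? |
|---|---|---|---|
| 5.5, continued follow-up | Missed treatments or missed seizures | No | No |
| 5.8.1, primary outcome from all patients | Any level of treatment compliance | No | No |
| 5.1.5, clinical ratings | Last treatment session | No | No |
| 5.1.5, cognitive battery | End of, or withdrawal from, treatment | No | No |

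The 5.1.5 and 5.8.1 provisions may recover some end-of-treatment data. None is stated to override section 5.6.

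**The plan's own figures.** Inputs from sections 5.7.1 and 5.8.1: remission 50% against 35% at the margin, margin 0.15, one-sided alpha 0.05, power 80%, 130 per arm.

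- n per arm = (0.50×0.50 + 0.35×0.65) × (1.645 + 0.842)² / 0.15² = 131.2, so 132 per arm (264 in total). The planned 260 is close to this.
- At 130 per arm, power is 79.7% with this variance and 78.0% if both true rates are 50%.
- AMT power for a 25-point difference (two-sided 0.05, normal approximation) is 98.4%, 98.9% and 99.9% for assumed rates of 62.5 v 37.5, 50 v 25 and 35 v 10. This agrees with the stated figure of more than 95%.

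**Possible bias.** If m of the n participants in an arm have no outcome, the full-data rate minus the available-case rate is

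(m/n) × (true rate in the missing − rate in the observed).

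The last factor cannot exceed 1 in size, so the arm rate moves by at most m/n. With equal arms of 130, the risk difference therefore moves by at most m/130 for m missing in total, however they split between arms.

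The documents give no rate of removal under section 5.6, so m is assumed. The upper value comes from the past-trial dropout figure in section 5.7.1 (below 3%): 0.03 × 260 = 7.8, so at most 7. That figure is not a 5.6 rate and serves only as an assumed ceiling.

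| m (assumed) | Outer limit, m/130 | All in one arm, true rate 20 points from observed | All in one arm, true rate 50 points from observed |
|---|---|---|---|
| 1 | 0.77 points | 0.15 | 0.38 |
| 3 | 2.31 points | 0.46 | 1.15 |
| 7 | 5.38 points | 1.08 | 2.69 |

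The 20- and 50-point gaps are also assumptions. If nobody is removed, the shift is zero.

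**Power with seven missing in one arm** (123 v 130): 98.1%, 98.7% and 99.8% for the same three rate pairs. Power is not the issue.

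**The case against.** The best reply is that the sections should be read together. Anyone removed mid-course also stops treatment, so the cognitive battery in section 5.1.5 is arguably due at that point, as are clinical ratings within four days. Section 5.8.1 also plans to obtain the primary outcome whatever the treatment compliance. On that reading, only the exploratory six-month visit is clearly unsecured. This has force for removals during treatment. It still leaves sites with a mandatory removal rule and no instruction that these assessments survive it.

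Secondly, 5.6(3) need not be applied at the first missed rating. The protocol is lenient elsewhere: patients unable to complete biomarker testing are kept (5.5), treatments missed through failed COVID screening do not count (8.6.1), telephone is a fallback for ratings during treatment (8.2), and AMT collection is prioritised (8.4). These show good intent, but none limits 5.6(3).

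Thirdly, little may be recoverable. A safety removal will sometimes rule out assessment, catatonia will often prevent testing, and a persistently absent participant may not return. That stands, so only part of the missing data is avoidable.

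Fourthly, the number of removals is assumed. In addition, section 5.7.1 starts the analysis once 260 participants have had an adequate trial, so ITT arms may exceed 130 and each participant's effect would then be smaller. Both points stand. Finally, Appendix B and the study SOPs were not available and could define non-compliance or contact after removal.

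**Conclusion.** The concern holds on the protocol text. Section 5.6 requires removal from the study for four reasons other than withdrawn consent, and no section states that outcomes are collected afterwards. Criterion (3) is the main fault, because it conflicts with the intention-to-treat approach in section 5.5.

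The effect is of unknown size and probably small: at most 0.77 points on the risk difference per missing outcome with 130 per arm, and at most 5.4 points for seven. With all seven in one arm and a true rate 20 to 50 points from the observed rate, it is 1.1 to 2.7 points. The removal counts and gaps are assumptions.

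The Stage 2 AMT test is the primary analysis exposed. The Stage 1 ITT analysis and the exploratory six-month data are also affected, while the Stage 1 primary analysis is largely untouched. The gap for 5.5(1) to (3) is minor, since those participants leave treatment rather than the study and section 5.8.1 already points towards collecting their primary outcome. The change should be made because it is cheap and protects a primary ITT analysis.

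**What to change.** Leave every decision to stop treatment as it is, and change the wording as follows.

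- **5.6(3):** replace it with a statement that missed visits or assessments are recorded as missed and do not lead to removal from the study.
- **5.6(2), (4) and (5):** state that these participants stop study treatment but are still asked for the post-acute and six-month assessments, remotely where needed, provided that they agree, have capacity and the investigator considers it safe.
- **5.5:** extend the continued-follow-up sentence to criteria (1) to (3), for consistency with section 5.8.1. This is mostly tidying.

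The cost is protocol wording and some extra contact effort. The visits are already scheduled, and section 8.2 allows the HRSD-24, SSI and AMT to be done by video. Recovery will be partial, for the reasons given above.

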5.7 Data Collection and Statistical Considerations

5.7.1 Power Calculations for primary hypotheses

The primary objective of this trial is to assess the efficacy and cognitive adverse effects of RUL-UB ECT and MST in patients with severe depression in a randomized, multi-centre, non-inferiority clinical trial. We will use a combined primary effectiveness endpoint: (1) MST will result in remission rates on the 24-item Hamilton Rating Scale for Depression (HRSD-24) that is non-inferior to that of RUL-UB ECT; **AND** (2) MST will have a superior cognitive adverse effect and tolerability profile compared to RUL-UB ECT assessed with the AMT. However, our sample size calculation will be based on non-inferiority trial calculations that are sufficiently large enough to minimize Type II error[103] and are consistent with previous large, multi-centre ECT trials[9]. RUL-UB ECT can achieve remission in about 50% of patients with a treatment resistant form of depression[10]. Non-inferiority trials such as this proposed study specify a tolerance threshold, with a tolerance of 15% denoting equivalence between the two treatments when the effectiveness of MST can be concluded to be not less than 35%. The total sample size is derived as a function of tolerance and power with a significance level of 0.05. Using these methods, a total sample size of 260 participants (130 per group) will yield 80% power to confirm a non-inferior difference in HRSD-24 remission rates of 15% between the two study groups. This sample size would also provide >95% power to detect a minimally important difference $\geq 25\%$ (absolute risk difference) change on the AMT total score. The primary analysis will proceed once a minimum of 260 participants achieve a clinically determined adequate trial of treatment. We will define a completer as any participant who has received an adequate trial of RUL-UB-ECT or MST as per the definition used in the literature by Sackeim and colleagues [10] (i.e., 8 treatments or meet remission criteria). The overall rate of dropout in a similar past trial at CAMH was less than 3 percent in those receiving fewer than 8 treatments. As such, the sample size of 260 completers will be attainable. Testing of the cognitive outcome will only proceed if non-inferiority is established on remission. This closed testing procedure will ensure the Type I error probability for these two outcomes does not exceed 0.05.

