5.0 APPROACH

5.1.1 Research Design and Methods

The trial will be registered in an international clinical trial registry (clinicaltrials.gov) and results will be reported in a manner consistent with the international CONSORT guidelines. The study will involve a randomized, double blind, parallel-group clinical trial with two treatment arms conducted at three leading academic institutions in North America: CAMH, University of Texas Southwestern in Dallas, and University of California, San Diego (UCSD). Based on our power analysis (Section 5.7.1), a total of 260 participants with depression will be randomized to receive MST or RUL-UB-ECT. We plan to enroll four to five participants per month across the three study sites over 54 months.

Treatment will be administered two to three days per week. Depression symptoms will be assessed with the 24-item Hamilton Depression Rating Scale (HRSD-24) [74] and suicidality will be assessed with the Scale for Suicidal Ideation (SSI) [69]. Remission will be defined as HRSD-24 ≤ 10 and a $> 60\%$ decrease in scores from baseline on two consecutive ratings. Once a participant reaches remission, a second rating to confirm remission will be conducted immediately before their next scheduled treatment. If remission is confirmed, they will then be considered a completer of the acute treatment course. Remission of suicidal ideation is defined as a score of 0 on the SSI. Therefore, there will be no specific minimum number of treatments that patients must receive to be classified as remitters. However, patients who do not meet remission criteria after 21 treatment sessions will be considered non-remitters and will cease treatment sessions. This maximum treatment number was chosen allowing for the possibility that MST may require more treatment sessions to achieve remission, similar to RUL-UB ECT [29-31]. The blind will not be broken to participants until the completion of the entire study. Following completion of the acute treatment course, participants who achieve response (defined as a 50% reduction in symptoms on the HRSD-24 from baseline) or remission will be referred to a maintenance treatment trial.

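### 260 is given both as the number randomised and as the minimum number of completers, with no allowance for early loss

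*Combined protocol and SAP*

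**What the plan says.** Section 5.1.1, citing the power analysis, states that "a total of 260 participants with depression will be randomized to receive MST or RUL-UB-ECT". Section 5.7.1 gives the calculation: "a total sample size of 260 participants (130 per group) will yield 80% power to confirm a non-inferior difference" of 15 percentage points in HRSD-24 remission.

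The same section then applies the number to a different population. It says: "The primary analysis will proceed once a minimum of 260 participants achieve a clinically determined adequate trial of treatment". A completer is someone with an adequate trial ("i.e., 8 treatments or meet remission criteria"). On loss, it says: "The overall rate of dropout in a similar past trial at CAMH was less than 3 percent in those receiving fewer than 8 treatments". It concludes: "As such, the sample size of 260 completers will be attainable".

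Section 5.8.1 makes the completer analysis primary for Stage 1, the non-inferiority test on remission, and also performs an analysis of all randomised participants. Section 5.5 lists reasons for stopping treatment, several of which can arise before the eighth session. No section gives a randomised total above 260 or provides for replacing non-completers.

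**The concern.** The number randomised and the number completing can be equal only if every randomised participant completes. The plan expects some loss, so at least one of the two sizes is wrong as written.

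Two things depend on which one is meant. The first is when recruitment stops and the primary analysis may start. The second is the size of the Stage 1 completer set, on which the decisive test is run and to which the stated power should refer. The size of the all-randomised set is left open as well.

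**Working it through.** **Inputs.** Section 5.7.1 gives 130 per arm, significance level 0.05, 80% power, early dropout below 3%, and ECT remission: "RUL-UB ECT can achieve remission in about 50% of patients with a treatment resistant form of depression". Section 5.8.1 gives the 15-point margin and the one-sided Z-test. The plan gives neither the MST remission rate assumed for the power calculation nor the variance formula, so two versions are shown.

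**Step 1: the plan's own 80%.** Power = Φ(0.15/√(V/n) − 1.645), with n per arm and V the sum of the two binomial variances.

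- 50% in both arms, true difference zero: V = 0.25 + 0.25 = 0.50. At n = 130, √(0.50/130) = 0.0620, 0.15/0.0620 = 2.419, and Φ(2.419 − 1.645) = Φ(0.774) = **78.0%**.
- Variances taken at 50% and 35%: V = 0.25 + 0.2275 = 0.4775. At n = 130, √(0.4775/130) = 0.0606, 0.15/0.0606 = 2.475, and Φ(0.830) = **79.7%**.

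The n per arm for a full 80% is V(1.645 + 0.842)²/0.15². This gives 137.4, so 138 per arm (276 in total), in the first version, and 131.2, so 132 per arm (264 in total), in the second. Neither returns exactly 130 per arm. Both put the power at 130 within 2 points of the stated 80%, and both do so with no dropout.

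**Step 2: 260 is the number randomised.** At 3% loss, 260 × 0.97 = 252.2, so about 252 completers, or 126 per arm. The trigger of 260 is not reached. With 50% in both arms, √(0.50/126) = 0.0630, 0.15/0.0630 = 2.381, and Φ(2.381 − 1.645) = Φ(0.736) = **76.9%**.

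The gap from the stated figure is 80 − 76.9 = 3.1 points. Of this, 80 − 78.0 = 2.0 points exist before any loss, and 78.0 − 76.9 = 1.1 points come from the loss. If each participant independently had a 3% chance of early loss, the chance that all 260 complete would be 0.97^260 = 0.0004, or 0.04%.

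**Step 3: 260 is the number of completers.** The number to randomise is 260/0.97 = 268.04, so **269**, which is 9 more than Section 5.1.1 states. Section 5.1.1 plans four to five enrolments a month for 54 months, which is 4 × 54 = 216 to 5 × 54 = 270. The 269 fits only at the top of that range.

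**The case against.** The strongest reply is that Section 5.7.1 sets a minimum and Section 5.1.1 never calls 260 a cap. Recruitment could continue until 260 complete. The trigger would then be reachable, dropout would cost no power, and the upper end of planned accrual would just cover it. The plan also considers dropout and judges 260 completers attainable. All of this stands, but it does not remove the inconsistency: on that reading about 269 are randomised, and Section 5.1.1 states 260.

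A reader might infer more than the documents support:

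- **That the trial cannot start its primary analysis.** This follows only if 260 is a cap, which the plan does not say.
- **That dropout is why 80% is missed.** At the plan's own rate it costs about 1 point. The larger part of the gap is there with no dropout and depends on an equal 50% remission rate that the plan does not state. With 50% and 35% variances, power at 130 per arm is 79.7%.
- **That the loss of power is substantial.** At an assumed 10% loss (117 per arm), power would be 74.2%, but no such rate appears in the documents.
- **That power is really about 68%.** That is the figure at 130 per arm if the 95% limit decided. Section 5.8.1 reports a 95% interval, but the test is one-sided and the level is 0.05, which corresponds to the 90% interval.
- **That the trigger biases the result, because remission can confer completer status.** The dependence is real, but no effect on error rate or power has been shown.

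**Conclusion.** The inconsistency is real and should be corrected. Sections 5.1.1 and 5.7.1 use 260 for two populations that can coincide only with zero early loss, so the stopping point of recruitment and the size of the Stage 1 completer set contradict each other.

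Its size is modest: either about 8 completers fewer than the trigger requires (260 − 252), or 9 more randomised than stated. These figures take the plan's upper bound of 3%, from one past trial at one of the three sites, as the loss rate. The power figures also rest on the normal approximation, balanced arms and the assumed remission rates. The stated 80% is slightly optimistic for the set analysed, but is not a serious error.

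**What to change.** Put one statement in both Section 5.1.1 and Section 5.7.1.

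- **Without extra patients:** 260 randomised. Delete the completer-count trigger. Run the primary analysis once the last randomised participant has had, or has missed, the post-acute assessment in Appendix A, Table 1. Restate power as about 78% for all randomised and about 77% for completers at 3% loss, giving the assumed MST remission rate, the margin and the one-sided 0.05 level beside it.
- **If 260 completers are intended:** keep that target in Section 5.7.1, state about 269 randomised at 3% loss in Section 5.1.1, and say that recruitment continues until the target is met.

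The first option costs only protocol wording and a slightly less favourable stated power. The second costs about 9 more participants at 3% loss, and more if loss is higher.
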